#### 6.4.4. Study variables

The following **sociodemographic variables** will be collected from patients' medical records or directly from patients during the study visit, straight after their inclusion in the study:

- Age
- Gender
- Race (caucasian, asiatic, latin, black, other)
- Level of education (uneducated, primary education, secondary education, university education)
- Working status (student, self-employed, employed by other, retired, housework, unemployed, temporarily unable to work, permanently unable to work, other)
- Smoking habits (non-smoker, ex-smoker, smoker, number of cigarettes per day)
- Alcohol intake (units per week).

The following **clinical variables** will be collected from patients' medical records (when available) or directly from patients during the study visit, straight after their inclusion in the study:

- Date of diagnosis (UD or CD).
- Disease activity at the beginning of the reference period and at the study visit through collection of the following variables:
  - For UC patients:
    - Partial Mayo Score (PMS) (9 point scale that excludes the endoscopic appearance of the mucosa)
    - General disease activity:
      - Mild: up to four bloody stools daily and no systemic toxicity
      - Moderate: four to six bloody stools daily and minimal toxicity
      - Severe: more than six bloody stools daily and signs of toxicity, such as fever, tachycardia, anaemia, raised erythrocyte sedimentation rate.
      - Fulminant: More than ten bloody stools daily, continuous bleeding, anaemia requiring blood transfusion, abdominal tenderness and colonic dilatation on plain abdominal radiographs.
    - Disease anatomic extent: proctitis, left-sided colitis or pancolitis.
    - Endoscopy findings:

- Normal or inactive disease
- Mild disease (erythema, decreased vascular pattern, mild friability)
- Moderate disease (marked erythema, lack of vascular pattern, friability erosions)
- Severe disease (spontaneous bleeding, ulceration).
- For CD patients:
  - Harvey-Bradshaw Index (HBI) (a simplified version of CDAI)
  - General disease activity:
    - Mild to moderate: ambulatory patients able to tolerate oral alimentation without manifestations of dehydration, toxicity, abdominal tenderness, painful mass, obstruction or >10% weight loss.

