    - Moderate to severe: failure to respond to treatment for mild disease, more prominent symptoms of fever, weight loss, abdominal pain or tenderness, intermittent nausea and vomiting without obstruction, or significant anemia.
    - Severe to fulminant: persisting symptoms on corticosteroids, high fevers, persistent vomiting, evidence of intestinal obstruction, rebound tenderness, cachexia, or evidence of abscess.
  - Disease behaviour: non-stricting and non-penetrating, stricturing and penetrating (fistulas and abscesses),
  - Disease location: terminal ileum.
- For CD and UC patients:
  - Stool frequency (normal number for this patient, 1-2 stools more than normal, 3-4 more stools than normal, 5 or more stools than normal)
  - Rectal bleeding (no blood seen, streaks of blood with stool less than half the time, obvious blood with stool most of the time, blood alone passes)
  - Urgency (hurry, immediately, incontinence)
  - Nocturnal stools (yes/no)
  - Need for antidiarrheal drugs (yes/no)
  - Constipation (yes/no)
  - Abdominal tenderness (none, mild and localized, mild to moderate and diffuse, severe or rebound)
  - Abdominal pain or cramping (none, mild, moderate, severe)
  - Anorexia (yes/no)
  - Nausea (yes/no)
  - Vomiting (yes/no)
  - Fever (yes/no)
  - Appetite loss
  - Weight loss (yes/no)
  - Fatigue (yes/no)
  - Night sweats (yes/no)

- Stunted growth (yes/no)
- Primary amenorrhoea (yes/no)
- General well-being (generally poor, fair, poor, terrible)
- Physician's global assessment (normal or quiescent disease severity, mild disease activity, moderate disease activity, severe disease activity)
- Other complications: severe profuse bleeding, massive bleeding due to ulceration, presence of stomach or duodenum ulceration, intestinal perforation, intraabdominal abscesses, stenosis, obstruction, fistulas, megacolon, others.
- Extraintestinal manifestations in UC and CD patients to be chosen from the following list according to ECCO guidelines:
  - Arthropathy and arthritis
  - Metabolic bone disease
  - Eye disease
  - Oral, aural and nasal disease
  - Skin disease
  - Hepato-pancreato-biliary disease
  - Neurological disease
  - Cardiovascular manifestations of IBD
  - Pulmonary manifestations of IBD

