- Urogenital manifestations of IBDComorbidities in UC and CD patients (defined as the coexistence of another medical condition alongside IBD, and does not imply causation) at the time of diagnosis and at the study visit, will be listed according to chosen according to the Charlson index:

Comorbidity Component	Score
Myocardial Infarction	1
Congestive Heart Failure	1
Peripheral Vascular Disease	1
Cerebrovascular Disease	1
Dementia	1
Chronic Obstructive Pulmonary Disease	1
Connective Tissue Disease	1
Peptic Ulcer Disease	1
Diabetes Mellitus	1 (mild), 2 (moderate- severe)
Moderate-Severe      Chronic      Kidney Disease	2
Hemiplegic	2
Leukemia	2
Malignant Lymphoma	2
Solid Tumor	2 (tumor), 6 (if metastasis)
Liver Disease	1 (mild), 3 (moderate-severe)
Acquired immunodeficiency syndrome (AIDS)	6

- Biological treatment/s for UC or CD followed during the reference period:
  - Starting date
  - Posology
  - Intensification of biological treatment: date and type of intensification
  - Continuing with the treatment
  - Date and reason for discontinuation, if applicable
  - New biological treatment prescribed after discontinuation, starting date, posology, continuing with the treatment, date and reason for discontinuation.
- Concomitant treatment with corticosteroids (e.g. prednisone, hydrocortisone, betamethasone, methylprednisolone, etc,) or immunosuppressives (e.g. Ciclosporin, Methotrexate, etc) during induction phase
  - Starting date, number of cycles

Other treatments followed before the reference period to be chosen from the following list:

- Aminosalicylates (e.g. mesalazine, Sulfasalazine, 5-ASA, etc), oral, enema, suppository.
- Corticosteroids (e.g. prednisone, hydrocortisone, betamethasone, methylprednisolone, etc), oral, enema, suppository.
- Thiopurines (e.g. azathioprine, mercaptopurine, etc).
- Immunosuppressives (e.g. Ciclosporin, Methotrexate, etc).
- Anti-diarrheal drugs.
- Pain medications.
- Antidepressants.
- Antibiotics.
- Use of alternative medicine (e.g. acupuncture, relaxation therapy, Qigong, herbal therapy, etc).
- Other (specify)

- Other treatments followed during the reference period to be chosen from the following list:
  - Aminosalicylates (e.g. mesalazine, Sulfasalazine, 5-ASA, etc), oral, enema, suppository.
  - Corticosteroids (e.g. prednisone, hydrocortisone, betamethasone, methylprednisolone, etc), oral, enema, suppository. Number of cycles
  - Thiopurines (e.g. azathioprine, mercaptopurine, etc).

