5.3. Disease characteristics

The analysis of continuous variables included the following variables:

- Time from diagnostic of disease (UC or CD) (time in months from the date of diagnostic until the date of informed consent).
- Charlson index.

The analysis of categorical variables included the following variables:

- Disease location (L1=terminal ileum; L2= colon; L3=ileum and colon; L4=upper gastrointestinal track; E1=proctitis; E2=left colitis; E3=extensive colitis).
- Disease behavior (only for CD patients) (B1=inflammatory; B2=stenosis; B3= fistulizing; B1p; B2p; B3p (p=perineal)).
- Extraintestinal manifestations:
 - Arthropathy and arthritis (yes/no).
 - Metabolic bone disease (yes/no).
 - Eye disease (yes/no).
 - Oral, aural and nasal disease (yes/no).

- Skin disease (yes/no).
- Hepato-pancreato-biliary disease (yes/no).
- Neurological disease (yes/no).
- Cardiovascular manifestations of IBD (yes/no).
- Pulmonary manifestations of IBD (yes/no).

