7.3. Secondary efficacy endpoints

- Secondary endpoint: Evaluate the impact of Extraintestinal Manifestations profile in IBD patients on treatment response to biological therapy.

The analysis that will be performed to answer the objective will be the following:

To evaluate the impact of extraintestinal manifestations profile in IBD patients on treatment response to biological therapy, a logistic regression analysis will be performed, in which **lack of response during the induction phase** will be used as the dependent variable and patient disease (CD or UC) and different extraintestinal manifestations variables (arthropathy and arthritis, metabolic bone disease, eye disease, oral, aural and nasal disease, skin disease, hepato-pancreato-biliary disease, neurological disease, cardiovascular manifestations of IBD,

pulmonary manifestations of IBD) will be used as independent variables, yielding the following results: Odds Ratio, 95%CI, p-value, sensitivity and specificity.

We will repeat this analysis with the **loss of response during the maintenance phase variable** as dependent variable.

- **Secondary endpoint: Describe the percentage of IBD patients exhibiting co-morbidities.**

The analysis that will be performed to answer the objective will be the following:

We will provide the frequencies, percentages and 95%CI of the following comorbidities for patients with Crohn's Disease and Ulcerative Colitis separately:

- Myocardial Infarction (yes/no).
- Congestive Heart Failure (yes/no).
- Peripheral Vascular Disease (yes/no).
- Cerebrovascular Disease (yes/no).
- Dementia (yes/no).
- Chronic Obstructive Pulmonary Disease (yes/no).
- Connective Tissue Disease (yes/no).
- Peptic Ulcer Disease (yes/no).
- Mild Chronic Hepatopathy (yes/no).
- Diabetes Mellitus (yes/no).
- Hemiplegic (yes/no).
- Moderate-Severe Chronic Kidney Disease (yes/no).
- Diabetes with lesions in target organs (yes/no).
- Solid Tumor (yes/no).
- Leukemia (yes/no).
- Lymphoma (yes/no).
- Moderate-Severe Chronic Hepatopathy (yes/no).
- Solid tumor with metastases (yes/no)
- Acquired immunodeficiency syndrome (AIDS) (yes/no).

- **Secondary endpoint: Determine the co-morbidities profile according to the level of IBD severity.**

The analysis that will be performed to answer the objective will be the following:

We will classify the patients into IBD severe or non-severe at baseline based on the HBI and PMI scores according the following criteria:

Harvey-Bradshaw Index score

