APPENDIX 1: INDEX OF SECTION 14 FOR THE CLINICAL REPORT

The following proposal for section 14 is done according to the pre-defined ICH-format. Minor changes from this planned index do not need to be amended in the SAP.

Comments in **Italics** will not be printed in table headers or footers.

Formal organization of tabulations may be changed during programming if appropriate, e.g., tables for the different variables may be combined into a single table, or tables with more than one variable may be split into several tables.

	TITLE	TABLE TYPE	ANALYSIS SET	COMMENT
14.	TABLES, FIGURES AND GRAPHS REFERRED TO BUT NOT INCLUDED IN THE TEXT			
14.1	DEMOGRAPHIC AND BASELINE DATA			
14.1.1	Subject disposition	CAT2	General population	
14.1.2	Subject characteristics			
14.1.2.1	Gender, Race	CAT2	Study population	
14.1.2.2	Level of education	CAT2	Study population	
14.1.2.3	Working status	CAT2	Study population	
14.1.2.4	Smoking habits / Alcohol abuse	CAT2	Study population	
14.1.3	Disease characteristics			
14.1.3.1	Time from diagnostic of disease	CONT2	Study population	
14.1.3.2	Charlson index	CONT2	Study population	

TITLE		TABLE TYPE	ANALYSIS SET	COMMENT
14.1.3.3 Disease location		CAT2	Study population	
14.1.3.4 Disease behavior		CAT2	Study population	
14.1.3.5 Extraintestinal manifestations		CAT2	Study population	

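### The SAP does not say when an extraintestinal manifestation must have been present, so one that began after treatment failed can be counted as a predictor of that failure

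*Protocol*

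**What the plan says.** Protocol 6.4.4 takes clinical variables from the medical record when available, or "directly from patients during the study visit, straight after their inclusion in the study". Three items in that section differ in how they are timed:

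- Disease activity has two time points: "Disease activity at the beginning of the reference period and at the study visit through collection of the following variables".
- Comorbidities have two others: "at the time of diagnosis and at the study visit, will be listed according to" the Charlson index.
- EIMs have none in their own line: "Extraintestinal manifestations in UC and CD patients to be chosen from the following list according to ECCO guidelines".

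SAP 5.3 lists nine EIM categories as yes/no variables. The first opens "Arthropathy and arthritis (yes/no", with no onset or reference date.

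SAP 7.3 fits a logistic model for lack of response in the induction phase. Its independent variables are disease type and "different extraintestinal manifestations variables (arthropathy and arthritis, metabolic bone disease, eye disease" and the remaining categories. The same model is then repeated for loss of response in the maintenance phase.

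SAP 7.1 places the first outcome 10 weeks after the start of anti-TNF treatment. It places the second at 6 months or later, with no upper limit.

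**The concern.** A predictor should be fixed before the outcome it is meant to predict. Here the outcome can be dated to week 10 or to some point after month 6, while the EIM value may describe the patient at a visit years later. If an EIM appears when the disease flares, it can be a result of losing response and still enter the model on the predictor side. The odds ratio would then be read as the impact of EIMs on response, which is how the first secondary objective is worded. Without a pre-treatment value in the database, the analyst cannot undo this afterwards.

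**Working it through.** **1. Is the time point fixed anywhere?**

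| Place | What it gives | Does it date the EIM? |
|---|---|---|
| Protocol 6.4.4, EIM item | Pick-list only | No |
| Protocol 6.4.4, disease-activity stem, if EIMs are nested under it | Two values: start of reference period and study visit | Only if the SAP names one of them, and it does not |
| SAP 5.3 | One yes/no per category | No |
| SAP Appendix 1, table 14.1.3.5 | Filed under "DEMOGRAPHIC AND BASELINE DATA" | No: SAP 5.3, whose variables fall under the same heading, measures time from diagnosis up to informed consent |
| SAP 7.3, EIM models | Yes/no predictors | No, whereas the severity analysis in the same section is explicitly at baseline |

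On either reading of the protocol, the value that enters the models is left open.

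**2. How long is the gap?** The biologic was started by June 2013 at the latest. The protocol's own reference list cites a 2016 consensus on EIMs, so visits fall about two and a half years or more after the latest start. The week-10 outcome is long past by then, and loss of response may be too.

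**3. How large could the distortion be?** The plan states no figure to reproduce for this point, and the documents give no EIM rates. All inputs below are assumptions.

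- p0 = EIM present at biologic start, equal in both outcome groups (no true effect): 10%, 20%, 30%.
- q_m = new EIM during follow-up in maintained responders: 3%, 5%.
- q_l = new EIM in patients losing response: 10%, 15%.
- Prevalence of the undated yes/no in a group = p0 + (1 - p0) × q.
- OR = [P_l / (1 - P_l)] / [P_m / (1 - P_m)].

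Lowest case (p0 30%, 5% vs 10%): P_m = 0.30 + 0.70 × 0.05 = 0.335 and P_l = 0.30 + 0.70 × 0.10 = 0.370. OR = (0.370/0.630) / (0.335/0.665) = 1.17.

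Highest case (p0 10%, 3% vs 15%): P_m = 0.10 + 0.90 × 0.03 = 0.127 and P_l = 0.10 + 0.90 × 0.15 = 0.235. OR = (0.235/0.765) / (0.127/0.873) = 2.11.

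All twelve combinations:

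| p0 | 3% vs 10% | 3% vs 15% | 5% vs 10% | 5% vs 15% |
|---|---|---|---|---|
| 10% | 1.61 | 2.11 | 1.38 | 1.81 |
| 20% | 1.35 | 1.63 | 1.23 | 1.49 |
| 30% | 1.24 | 1.44 | 1.17 | 1.35 |

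If new EIMs are equally frequent in both groups (for example 5% and 5%), P_m = P_l and OR = 1.0. An indicator limited to EIMs present at start also gives 1.0, because p0 was set equal.

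**4. Chance of a falsely significant result.** Take 200 patients, half losing response (assumed), and a two-sided 5% test of two proportions.

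- p0 20%, 5% vs 15%: 0.24 vs 0.32. SE = √(0.24×0.76/100 + 0.32×0.68/100) = 0.0632; z = 0.08/0.0632 = 1.265; chance ≈ Φ(1.265 - 1.96) = 24%.
- p0 20%, 5% vs 10%: 0.24 vs 0.28. SE = 0.0620; z = 0.645; chance ≈ Φ(0.645 - 1.96) = 9%.

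The calculation covers one EIM indicator and loss of response only. SAP 7.3 fits nine categories jointly with disease type, and nothing was computed for week-10 non-response.

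**The case against.** Several points on the other side are fair.

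- **Nesting.** The indentation in Protocol 6.4.4 allows EIMs to fall under the disease-activity stem. A value at the start of the reference period would then already be planned, and only one SAP sentence would be missing. This stands as a possibility and the fix allows for it. It does not remove the problem, because the SAP still names neither value.
- **Charts.** Protocol 6.1 prefers the chart over the patient's account where they disagree. The visit is when data are abstracted, not necessarily the date to which the value refers. That is true, but no reference date is set for the chart value either.
- **Baseline heading.** The SAP files EIMs under baseline data. This is some evidence of intent, but the material under that heading runs up to the date of consent.
- **Exploratory study.** SAP 5.1 calls the study descriptive. That limits the weight of the point, but the objective is still worded as impact.

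Two stronger readings are tempting. A reader might infer that EIMs caused by loss of response are being analysed as its predictors. The documents show only that nothing prevents it. A reader might also infer that overlap with the Charlson list is part of the same fault. Comorbidity is broadly "defined as the coexistence of another medical condition alongside IBD, and does not imply causation", and liver, joint, cardiac and lung conditions have a place in both lists. However, the overlap is of domain, not of identical items: comorbidities are confined to Charlson items, and the cardiovascular and pulmonary EIMs are limited to those of IBD. The missing rule on which list takes a condition is a separate, minor classification point that does not cause the timing problem.

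**Conclusion.** The point holds as a gap in timing. Neither document fixes when an EIM must have been present, and the same yes/no predicts two outcomes that may precede it. Both SAP 7.3 EIM models are affected, and so is the first secondary objective. The primary comorbidity models are not, since EIMs are not among their candidate variables in SAP 7.2.

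The size cannot be established from the documents. The range of 1.17 to 2.11 rests on assumed rates and on new EIMs being more common in patients who lose response; without that difference there is no bias. The change should be made before database lock, because a missing pre-treatment value cannot be recovered in the analysis.

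**What to change.** 1. Record from the chart whether each EIM was present before the first biologic dose. If the eCRF already holds a value for the start of the reference period, no new field is needed; name that value in the SAP.
2. State in SAP 5.3 and 7.3 that only this value enters both EIM models.
3. Report EIMs with later onset descriptively, by response group.

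The cost is one tick-box per EIM if not already collected, plus a few lines of SAP text. The downside is that fewer patients count as exposed, so estimates for rare categories become less precise.

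I would not add a comorbidity term to the EIM models as part of this change. Nine EIMs plus disease type already make 10 variables, the maximum assumed in Protocol 7.1, and one more makes 11. Comorbidities are also recorded at IBD diagnosis and at the study visit, not at biologic start, so such a term could bring the same timing problem back.

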#### **7.4. Assessment of the primary objective: Evaluate the impact of the co-morbidities profile in IBD patients on treatment response to biological therapy**

In order to determine the level of correlation between the co-morbidities profile and treatment response, adjusting for sociodemographic and clinical profile of patients, two logistic regression models will be conducted. The dependent variable of the models will be the lack of response during the induction phase (primary non response) and the loss of response during the maintenance phase (secondary loss of response) (see section 6.4.6). In both models independent variables will include all comorbidities included in the study, as well as sociodemographic and clinical variables as covariates. The maximum number of independent variables included in the model will be defined according to the number of patients per response category in the dependent variable. The maximum number of variables will be defined to ensure a minimum of 10 patients per independent variable and response category in the dependent one.

Depending on the volume of patients that have discontinued a biological treatment and started treatment with a different biologic during the reference period, this sample may be separately analyzed.

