## **7.6. Co-morbidities profile according to the level of IBD severity**

The percentage of patients reporting each co-morbidity at treatment initiation will be compared according to the IBD severity assessed using the PMS and the general disease activity for UC patients and the HBI and the general disease activity for CD patients. Multivariable regression models will be used to assess the relationship between the co-morbidities profile and the level of IBD severity.

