7.2. Primary efficacy endpoint

- **Primary endpoint:** Evaluate the impact of the co-morbidities profile in IBD patients on treatment response to biological therapy.

The analysis that will be performed to answer the objective will be the following:

In order to determine the level of correlation between the co-morbidities profile and treatment response, adjusting for sociodemographic and clinical profile of patients, two logistic regression models will be conducted. The dependent variable of the models will be the **lack of response during the induction phase and the loss of response during the maintenance phase**. In both models independent variables will include all comorbidities, as well as sociodemographic and clinical variables as covariates.

- The following potential variables will be considered for the analysis:
 - Crohn's Disease or Ulcerative Colitis.
 - Myocardial Infarction (yes/no).
 - Congestive Heart Failure (yes/no).
 - Peripheral Vascular Disease (yes/no).
 - Cerebrovascular Disease (yes/no).
 - Dementia (yes/no).
 - Chronic Obstructive Pulmonary Disease (yes/no).
 - Connective Tissue Disease (yes/no).
 - Peptic Ulcer Disease (yes/no).
 - Mild Chronic Hepatopathy (yes/no).
 - Diabetes Mellitus (yes/no).
 - Hemiplegic (yes/no).
 - Moderate-Severe Chronic Kidney Disease (yes/no).
 - Diabetes with lesions in target organs (yes/no).
 - Solid Tumor (yes/no).
 - Leukemia (yes/no).
 - Lymphoma (yes/no).

- Moderate-Severe Chronic Hepatopathy (yes/no).
 - Solid tumor with metastases (yes/no)
 - Acquired immunodeficiency syndrome (AIDS) (yes/no).
 - Gender.
 - Race (caucasian, asiatic, latin, black, other).
 - Level of education (uneducated, primary education, secondary education, university education).
 - Working status (student, self-employed, employed by other, retired, housework, unemployed, temporarily unable to work, permanently unable to work, other).
 - Smoking habits (non-smoker, ex-smoker and smoker).
 - Alcohol abuse (yes/no).
 - Time from diagnostic of disease.
 - Disease location.
 - Discontinuation the biological treatment (yes/no)
- Each one of the variables will be compared between the subjects with primary non-response vs primary response and primary response maintenance vs loss of response and those variables whose p-value is lower than 0.1 are considered potential variables for performing a logistic regression analysis.

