- Non severe (Remission <5; Mild disease 5-7; Moderate disease 8-16)
- Severe disease >16

Partial Mayo Index Score

- Non severe (Remission = 0-1; Mild Disease = 2-4; Moderate Disease = 5-7)
- Severe Disease =8-9

We will compare the percentage of patients reporting each co-morbidity between IBP severe or non-severe using Chi-Square.

A logistic regression analysis will be performed, in which **IBP severe or non-severe at baseline** will be used as the dependent variable and patient disease (CD or UC) and different comorbidities variables will be used as independent variables, yielding the following results: Odds Ratio, 95%CI, p-value, sensitivity and specificity.

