14.3 EFFICACY DATA			
14.3.1 Primary efficacy parameter			
14.3.1.1 Comparison of subjects presenting comorbidities, sociodemographic and clinical variables based on the lack of response during the induction phase (primary response vs primary non-response)	COMP1 / COMP4	Study population	
14.3.1.2 Logistic regression: Lack of response during the induction phase	RL	Study population	
14.3.1.3 Comparison of subjects presenting comorbidities, sociodemographic and clinical variables based on the loss of response during the maintenance phase (primary response maintenance vs loss of response)	COMP1 / COMP4	Study population	
14.3.1.4 Logistic regression: Loss of response during the maintenance phase	RL	Study population	

TITLE	TABLE TYPE	ANALYSIS SET	COMMENT
14.3.2	Secondary efficacy parameters		
14.3.2.1	Logistic regression: Lack of response during the induction phase based on the extraintestinal manifestations	RL	Study population
14.3.2.2	Logistic regression: Loss of response during the maintenance phase based on the extraintestinal manifestations	RL	Study population
14.3.2.3	Comorbidities description according to IBD	CAT2	Study population
14.3.2.4	Comparations of comorbidities between IBD severe vs non-severe at baseline	COMP1	Study population
14.3.2.5	Logistic regression: IBD severe or non-severe at baseline based on the comorbidities and patient disease	RL	Study population

TYPES OF TABLES

Examples for descriptive analysis of categorical variables:

CAT2

		Variable 2						
		Value a		Value b		...		
Variable 1	Value a	N	%	N	%	N	%	Total
	Value b							
	...							
	Total							

Examples for descriptive analysis of continuous variables:

CONT2

			Variable 1			
			N	Mean	Median	Standard deviation
Variable 2	Value a					Minimu
	Value b					m
	...					

Examples for multivariable analysis or comparations:

Chi-square results

COMP1

	Value	df	Asym. Sig. (2-sided)	Exact Sig. (2-sided)	Exact Sig. (1-sided)
Pearson Chi-square					
Continuity correction					
Likelihood Ratio					
Fisher's Exact Test					
Linear by linear association					
N of valid cases					

T-test results

COMP 4

Independent Samples Test

			Variable	
			Equal variances assumed	Equal variances not assumed
Levene's Test for Equality of variances	F			
t-test for Equality of means	t			
	df			
	Sig. (2-tailed)			
	Mean Difference			
	Std. Error Difference			
	95% Confidence Interval of the difference		Lower	Upper

Logistic regression results

LR

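### Comorbidity, the primary exposure, is recorded at diagnosis and at the study visit but analysed as of biologic start in Protocol 7.6 and without any date in the primary models

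*Protocol*

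**What the plan says.** Protocol 6.4.4 defines two comorbidity records. Comorbidities "at the time of diagnosis and at the study visit, will be listed according to chosen according to the Charlson index". The only diagnosis date in that section is the date of UC or CD diagnosis. The start date of the biologic is a separate item, and no onset date is listed for any comorbidity.

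Protocol 7.6 uses a third time: "The percentage of patients reporting each co-morbidity at treatment initiation will be compared according to the IBD severity".

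Protocol 7.4, on the primary objective, gives no time: "In both models independent variables will include all comorbidities included in the study, as well as sociodemographic and clinical variables as covariates". SAP 7.2 repeats this almost word for word and lists each Charlson condition as a yes/no candidate without a date. In the SAP 7.3 severity model, severity is classified at baseline, while "patient disease (CD or UC) and different comorbidities variables will be used as independent variables", again undated.

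Disease activity is handled differently. Protocol 6.1 and 6.4.4 collect it when the biologic starts and again at the visit.

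**The concern.** Comorbidity is the exposure of the primary objective, and Protocol section 4 presents the study as a step towards predicting response to biological treatment. A predictor has to be fixed before the outcome it predicts. Here two records exist, neither is dated to biologic start, and the models do not choose between them.

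If the visit record is used, a condition that appeared after week 10, or after response was lost, counts as a predictor of that earlier event. If the diagnosis record is used, conditions acquired between diagnosis and biologic start are missed. Because no rule is written, the choice could also be made after the data are seen.

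**Working it through.** **1. The plan's own figure.** Protocol 7.1 asks for 10 events per variable, at most 10 variables and 50% non-response: 10 × 10 / 0.50 = 200 per disease. This reproduces and is not in dispute; exposure timing does not change it.

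**2. Which time each place uses.**

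| Place | Comorbidity time |
|---|---|
| Protocol 6.4.4 (collection) | diagnosis; study visit |
| Protocol 7.6 (severity comparison) | treatment start |
| Protocol 7.4, SAP 7.2 (primary models) | not stated |
| SAP 7.3 (severity model) | not stated |

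The time required by 7.6 is not among those collected, and no rule connects them.

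**3. Gap between the week-10 outcome and the visit.** Biologics started between June 2011 and June 2013 (Protocol 3.8). Primary non-response is judged at 10 weeks (SAP 7.1). No visit date is given, so two floors are assumed: January 2015, from the year in the study code, and January 2016, because reference 33 of the protocol is dated 2016.

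The shortest gap belongs to the latest starter: 30 June 2013 + 70 days = 8 September 2013.

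- To 1 January 2015: 480 days / 30.4375 = 15.8 months.
- To 1 January 2016: 845 days / 30.4375 = 27.8 months.

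These are minimum gaps. Without a visit date there is no upper bound.

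For loss of response, Protocol 6.1 ends the reference period at the visit at the latest. A loss of response within that period therefore cannot come after the visit record, and will often precede it.

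**4. What can be recovered about status at biologic start.** Assume that conditions are permanent once present and that diagnosis precedes the biologic.

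| At diagnosis | At visit | At biologic start |
|---|---|---|
| positive | positive | positive |
| negative | negative | negative |
| negative | positive | cannot be placed |
| positive | negative | excluded by the assumption; query |

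**5. Can the bias be sized?** Not from the documents, which give no prevalence or incidence of any comorbidity. An illustration with assumed inputs shows that even the direction is open. Take prevalence p at biologic start and a rate r of new disease per year over t years, so that visit prevalence = p + (1 − p)(1 − exp(−rt)). Let p = 0.05 and t = 2.3 years (the January 2016 floor).

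- True odds ratio 1.0, with r = 0.01 in responders and 0.03 in non-responders: visit prevalence 0.072 and 0.113, apparent odds ratio 1.66.
- True odds ratio 2.0 (p = 0.05 in responders), with r = 0.01 in both groups: apparent odds ratio 1.70.

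The first creates an association and the second weakens one.

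**The case against.** The strongest reply is that many Charlson conditions are chronic, so the two records already bracket biologic start. That largely stands. A reader might infer that the 7.6 analysis cannot be run at all, but under permanence only the negative-then-positive patients are unresolved. What is missing is the rule and the handling of that group.

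A second reply is that the intended date is plain from 7.6 and from the way disease activity is collected, and that diagnosis in the garbled sentence of 6.4.4 is a drafting slip. That is possible but cannot be shown. It would still leave the primary models undated.

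The SAP's baseline wording does not settle the matter. The block headed "DEMOGRAPHIC AND BASELINE DATA" lists the Charlson index, not the single conditions that are modelled. In the table title "Comparations of comorbidities between IBD severe vs non-severe at baseline" the last words most naturally date severity. Even if they date the whole comparison, they do not reach the primary models.

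The eCRF is not among the documents, so a field for onset dates cannot be excluded. The SAP would still have to say that it is used.

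The visit dates are inferred. The 2016 reference may have entered in a revision: Protocol 6.3.2 cites number 33 for a 2010 guideline, while the reference list gives a 2016 paper under that number. A reader might infer that the visit follows week 10 by several years in every patient. On the cautious floor the documents support only about 16 months for the latest starters. The order of events does not depend on which floor is taken.

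**Conclusion.** The collection times and the analysis time contradict each other, and the primary exposure has no date. On either floor the visit record follows the week-10 outcome in every patient: by at least about 16 months from January 2015, or about 28 months from January 2016. An odds ratio built on that record could not be read as prediction of response.

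A reader might infer a known distortion of the odds ratios. The documents do not support one: its size and direction depend on rates that they do not give, and sampling error for rare conditions may well exceed it. As an assumed example, a condition present in 20 of 400 patients, with a true odds ratio of 2.0 and 50% non-response, has a Wald 95% interval of about 0.78 to 5.15. The point rests on the order of events and on the open choice of record. The recovery rule in the working rests on permanence of the conditions, which is also an assumption.

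**What to change.** Reconcile Protocol 6.4.4, 7.4 and 7.6 with SAP 7.2 and 7.3 on one exposure date, the start of the first biologic. That start date is already collected.

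- State in Protocol 7.4 and 7.6 and in SAP 7.2 and 7.3 that only comorbidities present at that date enter the models, and that the visit record is used for description only. The SAP introduction has the SAP signed before database lock, so the rule can be fixed in time.
- For patients negative at diagnosis and positive at the visit, take the onset date, or the status at biologic start, from the chart.
- Where the chart does not show it, run the model with those patients coded both ways and report both results.

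The cost is one extra chart-derived field for the discordant conditions, expected to be few, and a small sensitivity analysis. Protocol 9.2 already requires eCRF data to be traceable to the charts. The sample size does not change. Onset may be missing from some charts, which is why the two-way coding is needed.
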